The study is powered for the primary outcome of Area under the Curve (AUC) for pain from 0-48 hours. From review of the literature of previous studies, we deemed a margin of 80% of 48 hours to be non-inferior [24,25,]. A group sample size of 50 per cohort is needed achieve a 90% power to detect non-inferiority using a one-sided, Mann-Whitney test. The margin of non-inferiority is 38 (80% of 48 hours). The non-inferiority margin corresponds to an increase in pain, not a decrease. The pain VAS ranges from 0 to 10, with 10 being the worst pain. Therefore, non-inferiority will be declared if the average AUC for liposomal bupivacaine is no more than 38 units compared to the average AUC in the TEA group. The true difference between the means is assumed to be 0.0. The significance level (alpha) of the test is 0.025 and the data are drawn from populations with standard deviations of 55.0. These assumptions were derived from previous Pacira studies. It is reasonable to assume that the standard deviation of the AUC for 0-48 hours is about 55 units and the difference between the groups is 0. Sample size calculations were performed using PASS (PASS 16 Power Analysis and Sample Size Software (2018). NCSS, LLC. Kaysville, Utah, USA, ncss.com/software/pass). Of note, with sequential testing of the co-primary endpoints, the study remains to be adequately powered with the addition of the total opioid consumption co-primary endpoint. A sample size of 50 participants in each arm will have adequate power (>90%) to detect non-inferiority with a margin of 21.2 IV morphine equivalents using a one-sided test with a common standard deviation of 25 and alpha of 0.025. The non-inferiority margin was determined by the clinically significant threshold of 10.6 mg in daily IV morphine equivalent dose [24], therefore, 21.2 morphine equivalent dose for over 2 days (0-48 hours).

Intention to treat statistical analyses will be used to test the null hypothesis. Thus, if a patient has been randomized to the TEA arm of the trial and an epidural cannot be placed or cannot be used due to other circumstances (ie. persistent hypotension) the patient will receive the other elements of the ERAS multimodal pain bundle, which is consistent with our current clinical practice and that patient's data will be included in the dataset for the TEA arm in the final analysis. Additionally, in the event a participant wishes to drop out of the study prematurely postoperatively (ie. declines further blood/saliva collection and/or to fill out surveys), they will be allowed to do so and the data collected during their enrollment period will still be included in the dataset for their respective treatment arm unless they submit a formal written objection.

Secondary outcome variables:

T-tests or the nonparametric Mann-Whitney test will be used to compare normally and non-normally distributed data between the study arms. The log-rank test will be used to compare the time to (ROBF) as well as the time to postoperative diuresis to account for right censoring in which case no event (ROBF/diuresis) is observed within the observed time. A Poisson regression model will be used to compare the length of hospital stay. Chi-square tests will be used to compare the incidence of major postoperative complications between the two treatments. Chi-square tests will also be used to compare the incidence of major postoperative complications between the two treatments. Daily mean and median as well as mean baseline change in surgical stress biomarkers will be compared between treatment groups using t-tests or the Mann-Whitney test depending on whether data are normally or non-normally distributed. Average daily QoR-15 scores will be compared between the study cohorts.

b. Early stopping rules.

If there is concern for harm on either arm of the study this will be immediately discussed with the PI and the study will be stopped until the concern is resolved. The PI will internally monitor the progress of the trial, including review and confirmation of all safety/treatment-related outcomes, response assessments, safety reports and/or any related source documentation. As per above, the DSMB will meet after 20 patients have been enrolled in each arm. Regarding the futility boundary for the interim analysis – based on the results from the pilot study in 2019, the pain for the Epidural group and for the Exparel group are about the same (3.9 vs 4.0 in a 0-10 scale). With the O'Brien-Fleming futility boundary of 0.2986, there is only 0.1% chance of falsely crossing the futility boundary and stopping the study at 20 participants per arm assuming equal pain for both groups. The overall power remains to be over 90%. If in case that the Exparel group is truly inferior to the Epidural group by at least the pre-specified non-inferiority margin, there is at least a 38% chance of claiming early futility at 20 patients per arm to protect more patients from being exposed to the inferior treatment.

Interim analysis of toxicity, outcome and ongoing scientific investigations will be performed at least annually by the Sidney Kimmel Comprehensive Cancer Center Data Safety Monitoring Board (SKCCC DSMB). The SKCCC DSMB Recommendation letter will state the timeline for the next required review. The SKCCC DSMB will review aspects of this trial that are outlined in the responsibilities section of the Data and Safety Monitoring Board (DSMB) Guidance. If the committee decides that amendments should be made to this trial, recommendations will be made in writing to the Study Principal Investigator. The study team will submit modifications to the IRB within 60 days of receipt from the DSMB. The Associate Director of Clinical Research, will arbitrate any disagreements between the DSMB and the study Principal Investigator. These changes may include early termination of accrual if deemed appropriate. The SKCCC Compliance Monitoring Program will provide external monitoring for JHU-affiliated sites in accordance with SKCCC DSMP (Version 6.0, 02/21/2019). The SMC Subcommittee will determine the level of patient safety risk and level/frequency of monitoring.

1. Risks

- a. Medical risks, listing all procedures, their major and minor risks and expected frequency. The risks listed for liposomal bupivacaine surgical site infiltration and for thoracic epidural here and on the study consent are the same ones listed for patients on the 9/18 version of the Consent for Anesthesia and Anesthesia-Related Procedures that is routinely used for surgery here at Johns Hopkins for Regional Nerve Block and for Epidural Anesthesia, respectively.
 - Liposomal bupivacaine surgical site infiltration: Infection, soreness, bruising, weakness, persistent numbness or pain, injury to blood vessels or nerves, and, rarely, seizures or loss of consciousness.
 - Thoracic Epidural Analgesia: Headache or backache; infection; ringing in the ears; persistent or permanent weakness; numbness or pain; loss of sensation or other nerve functions, changes in my heart rate or blood pressure, and rarely paralysis or seizures.
- b. Steps taken to minimize the risks.
 - All TEA will be placed per institutional standard protocols.
 - All liposomal bupivacaine infiltration will be performed as outlined in the wound infiltration protocol (provided in supplemental materials)
 - As noted above, all surgical stress biomarkers obtained through blood draws will be drawn at already planned IV access for standard surgical care therefore no additional IV access for blood will be obtained.
 - All adverse events will be monitored by the PI and logged in the adverse event log. Adverse event definitions and severity have been defined prior to trial initiation.
- c. Plan for reporting unanticipated problems or study deviations.

All unanticipated problems or study deviations will be brought to the immediate attention of the PI. Study team research meetings, which will occur monthly during the duration of this study, will be used to further troubleshoot study deviations, problems or concerns raised by co-investigators. The PI will oversee all data and safety monitoring. The PI will internally monitor the progress of the trial, including review and confirmation of all safety/treatment-related outcomes, response assessments, safety reports and/or any related source documentation. The data and safety monitoring plan entails that the PI submit all safety and problem/event information to the IRB on a semi-annual basis. Further, as noted above, the DSMB will meet after 20 patients have been enrolled in each arm. Interim analysis of toxicity, outcome and ongoing scientific investigations will be performed at least annually by the Sidney Kimmel Comprehensive Cancer Center Data Safety Monitoring Board (SKCCC DSMB). The SKCCC DSMB Recommendation letter will state the timeline for the next required review. The SKCCC DSMB will review aspects of this trial that are outlined in the responsibilities section of the Data and Safety Monitoring Board (DSMB) Guidance. If the committee decides that amendments should be made to this trial, recommendations will be made in writing to the Study Principal Investigator. The study team will submit modifications to the IRB within 60 days of receipt from the DSMB. The Associate Director of Clinical Research, will arbitrate any disagreements between the DSMB and the study Principal Investigator. These changes may include early termination of accrual if deemed appropriate. The SKCCC Compliance Monitoring Program will provide external monitoring for JHU-affiliated sites in accordance with SKCCC DSMP (Version 6.0, 02/21/2019). The SMC Subcommittee will determine the level of patient safety risk and level/frequency of monitoring.

- d. Legal risks such as the risks that would be associated with breach of confidentiality.

CRFs will be organized in a binder for each patient participant. The binder will follow the patient with their inpatient chart throughout their perioperative journey. At the time of hospital discharge, the each CRF binder will be stored in a locked filing cabinet in the PI's office. Post-operative pain medication logs collected from patients in the outpatient setting at their first postoperative appointment will be given to the PI to file with the other CRFs in the patient's binder. All patient data will then be entered into a secure, password protected REDCap database housed on a JHED-enabled computer and only those listed as investigators on this study will have access to this database to minimize the risk of breaches of confidentiality.

- e. Financial risks to the participants.

There is no anticipated financial risk to the participants. Liposomal bupivacaine and surgical stress biomarker assays will be paid for by the study and will not be a cost to the individuals participating. There is no anticipated burden of extra cost to patients beyond what industry funding and standard perioperative care provide.

2. Benefits

- a. Description of the probable benefits for the participant and for society.

This study would be the first randomized trial comparing the value of the two prevailing modalities of loco-regional analgesia (TEA and LB surgical site infiltration) used by ERAS programs for open abdominal surgery in the U.S. The proposed value analysis is unique in accounting for a wide spectrum of quality, outcome and cost variables. Further, it has potential to set a precedent for quantifying the impact of discrete ERAS components on the surgical stress response. While the concept and theory behind surgical stress are old, little is known about its pathophysiology in the era of modern surgery. Results from this study would also better define the optimal non-opioid pain management regimen for patients recovering from

open abdominal surgery and are urgently needed by the American College of Surgeons and the Society of Gynecologic Oncology in formulating our national ERAS guidelines.

3. Payment and Remuneration

- a. Detail compensation for participants including possible total compensation, proposed bonus, and any proposed reductions or penalties for not completing the protocol.

Patients will be not be given any payment or compensation for participating in this study.

4. Costs

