Coprimary efficacy endpoints will be used to test the hypothesis that surgical site infiltration with LB is non-inferior to TEA: (1) the mean Area under the Curve (AUC) of visual analog scale (VAS) pain intensity scores from 0 to 48 hours postoperatively and (2) total opioid consumption (IV morphine equivalents, mg) from 0 to 48 hours postoperatively will be compared between the two treatment groups. The mean AUC of VAS pain intensity scores endpoint incorporates the use of rescue medications by using an imputation method called windowed worst observation carried forward (WWOCF). This method imputes a subject's pain score as their worst pain score for a pre-specified window after a rescue medicine. Subjects will be evaluated for pain intensity at rest at 6, 12, 18, 24, 30, 36, 42, 48, and 72 hours after surgery and then once daily (at noon \pm 4 hours) through postoperative day 14. Subjects will also record an unscheduled pain score immediately before any requested opioid pain medication. The exact time of the assessment will be recorded to limit variability. Total opioid consumption in IV morphine equivalents (mg) during the first 48 hours postoperatively will be tracked for each subject.

Secondary objectives:

To compare the impact of TEA and surgical site infiltration with LB on patient reported and clinical outcomes as well as on neuroendocrine and inflammatory mediators of the surgical stress response using the following measures:

1. Mean patient-perceived quality of recovery score on postoperative days 1-7 (QoR-15).
2. Time to return of bowel function (ROBF) and incidence of postoperative ileus.
3. Mobility Level.
4. Degree of sedation.
5. Length of hospital stay and time (in days) to meeting discharge criteria.
6. Total intravenous fluids administered and time to postoperative diuresis.
7. Need for vasopressors (amount and duration).
8. Incidence of major postoperative complications, including 30-day hospital readmission.

9. Total direct costs associated with loco-regional anesthesia.
10. Post-discharge narcotic utilization.

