1. Mean patient-perceived quality of recovery score on postoperative days 1-7. Patient-perceived quality of recovery will be assessed using the Quality of Recovery score (QoR-15) which is a validated instrument designed to measure the major domains of postoperative recovery including functional independence, physical comfort/pain, psychological/emotional well-being, cognition and satisfaction (Appendix A). Quality of recovery will be measured using this instrument on the first postoperative day and each day thereafter (at noon \pm 4 hours during a period of rest) during inpatient hospitalization to and including the day of discharge or postoperative day 7 (whichever comes first) in order to obtain longitudinal data about the quality of recovery experienced by patients. Patients unable to complete the questionnaire independently will be asked for verbal responses to each item.

2. Time to return of bowel function (ROBF) and incidence of postoperative ileus. Time to ROBF will be defined as the time lapse from the day of surgery (DOS) to the day oral intake is tolerated for 48 hours without vomiting. Ileus is defined as the occurrence of postoperative nausea and vomiting requiring cessation of oral intake and initiation of intravenous hydration +/- nasogastric tube placement following documented ROBF or the persistence of these symptoms beyond postoperative day 5 in the absence of ROBF.

3. Level of mobilization. Preoperative baseline mobility will be assessed using the Boston University AM-PAC Surgical Short Form per our standard practice. On the first postoperative day and each day thereafter through date of discharge or postoperative day 7 (whichever comes first), mobility will be assessed using the 8-point validated JH-HLM scale. Need for formal physiotherapy consultation will also be recorded.

4. Degree of sedation. Degree of sedation will be assessed on each postoperative day through the date of discharge or postoperative day 7 (whichever comes first) at noon \pm 4 hours using the Pasero Opioid Induced Sedation Scale (Appendix B).

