Because of the invasive nature of the interventions, neither the trial participants nor the investigators will be blinded to group allocation.

Visual analog scale (VAS) pain intensity scores will be collected from patients at rest at 6, 12, 18, 24, 30, 36, 42, 48, and 72 hours after surgery and then once daily (at noon \pm 4 hours) through postoperative day 14. Subjects will also record an unscheduled pain score immediately before any requested opioid pain medication. The exact time of the assessment will be recorded to limit variability. Total opioid consumption in IV morphine equivalents (mg) during the first 48 hours postoperatively will be tracked for each subject.

Pain scores obtained during the opioid medication-specific window (see table below) will be replaced with the worst observation carried forward (WWOCF). For subjects who take a rescue medication, their VAS pain scores recorded within the window of controlled type of rescue medication will be replaced by the “worst” observation. The worst observation will be the highest VAS score from the end of the previous rescue window or the end of surgery, whichever is later.

Opioid Rescue Medication Window		
Medication	Route	Window Used to Impute VAS
Oxycodone, Oxycocet, Percocet, acetaminophen-oxycodone, Oxycontin	PO, IM, IV, SC	6 hours
Morphine	IV, PO, SC	4 hours
Hydromorphone (Dilaudid), Hydromorphone hydrochloride	IV	2 hours
Hydromorphone (Dilaudid), Hydromorphone hydrochloride	PO, IM, SC	4 hours
Hydrocodone	PO	6 hours
Fentanyl	IV, PO, IM	6 hours
Hydrocodone combination product - Vicodin, Norco, Lorcet, Lortab, hydrocodone-acetaminophen	PO	6 hours
Codeine combination product - Tylenol 3, acetaminophen-coedine, Paracetamol Forte, Tylenol 4	PO	6 hours
Ultram, Tramadol, Tramadol hydrochloride	PO	6 hours
PO = oral, IV = intravenous, IM = Intramuscular, SC = subcutaneous,.		
If other rescue medications not listed above are given, the window will be determined post-hoc. If a combination opioid product is given, the window will be determined by the opioid part of the medication.		

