- c. Justification and safety information if non-FDA approved drugs without an IND will be administered.

7. Study Statistics

- a. Primary outcome variables:

The study has two co-primary endpoints: (1) the mean Area under the Curve (AUC) of visual analog scale (VAS) pain intensity scores from 0 to 48 hours postoperatively and (2) total opioid consumption (IV morphine equivalents, mg) from 0 to 48 hours postoperatively. The primary hypothesis will be assessed in joint hypothesis testing which controls the type I error at 0.025 across both non-inferiority tests; AUC for VAS pain scores and total opioid consumption through 48 hours postoperatively. Significance will need to be achieved for both co-primary endpoints.

For analyzing the AUC of the VAS pain assessment, we will use an approach that has been previously used in Pacira studies. The area under the curve (AUC) is derived using the trapezoidal rule (see formula below) using the adjusted and imputed VAS pain scores. The VAS scores will be adjusted for the use of rescue medication using the WWOCF approach. AUC will start with the first postsurgical pain assessment. All pain assessments through 48 hours after surgery, including both scheduled and unscheduled will be used in deriving AUC. Exact assessment times will be used in deriving AUC.

$$AUC = \left\{ \sum_{i=2}^n (p_i + p_{(i-1)})(t_i + t_{(i-1)}) \right\} / 2$$

The AUC for VAS may be analyzed using ANOVA with treatment group as a main effect and include other covariates as deemed reasonable. Based on the model, the LS Mean and SE will be reported for each treatment group. The 95% confidence interval for the difference between

treatment groups and the one-sided test performed at 2.5% level of significance will be inspected for non-inferiority.

Total opioid consumption over 48 hours postoperatively will be abstracted by our research assistant from the medical administration record (MAR) as it appears in the EMR for each patient.

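### No preoperative VAS pain score or QoR-15 is scheduled, so the pain co-primary and the first-listed secondary endpoint forgo a modest, cheap gain in precision

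*Combined protocol and SAP*

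**What the plan says.** - **Pain schedule.** Section 2 (Objectives) says "Subjects will be evaluated for pain intensity at rest at 6, 12, 18, 24, 30, 36, 42, 48, and 72 hours after surgery". Section 4a repeats the schedule. Both add unscheduled scores before requested opioids and daily scores to day 14. All of these are postoperative.
- **AUC derivation.** Section 7a: "AUC will start with the first postsurgical pain assessment".
- **AUC model.** Section 7a: "The AUC for VAS may be analyzed using ANOVA with treatment group as a main effect and include other covariates as deemed reasonable". No covariate is named. The sample size paragraph of the same section assumes a one-sided Mann-Whitney test.
- **QoR-15.** Section 2, secondary objective 1: "Quality of recovery will be measured using this instrument on the first postoperative day and each day thereafter". Section 4a repeats the daily collection and adds no preoperative form. The analysis, under secondary outcome variables, is "Average daily QoR-15 scores will be compared between the study cohorts", with no baseline term.
- **Baselines that are taken.** For mobility, "Preoperative baseline mobility will be assessed using the Boston University AM-PAC Surgical Short Form per our standard practice". Blood is drawn on the day of surgery when IV access is established, saliva is collected preoperatively, and biomarkers are analysed partly as change from baseline.

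**The concern.** Both outcomes are self-ratings, and patients differ in how they use such scales. Patients with some pain from their disease before surgery are eligible, since section 5 excludes only long-term opioid use for chronic pain. A patient's own preoperative score is therefore the covariate most specific to each outcome. If it is never recorded, it cannot enter the model, and balance between the arms on it cannot be shown. That cannot be repaired at the analysis stage.

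Non-inferiority on pain is decided by the upper end of one confidence interval. A prognostic baseline covariate narrows that interval without more patients and removes the part of a chance imbalance that carries through to the outcome. The question is how much this is worth here.

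**Working it through.** **Inputs from section 7a:** margin 38 AUC units, SD 55, true difference 0, one-sided alpha 0.025, 50 per arm, target power 90%. AUC is in point-hours, so the margin is 38/48 = about 0.8 points of average pain over 48 h.

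**Assumed input:** the correlation r between a preoperative VAS score and the AUC. The documents give none, so a range of 0.1 to 0.4 is shown.

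**Step 1: the plan's own figure.** The normal approximation for n per arm is 2 × 55² × (1.960 + 1.282)² / 38² = 44.02, so 45; the noncentral t gives 46. Dividing by the Mann-Whitney efficiency for normal data (3/π) gives 48 to 49. A simulated Mann-Whitney test at 50 per arm (20,000 runs) has power 91.4%, and the t-test has 92.8%. The stated 50 per arm for 90% power is reproduced without any covariate.

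**Step 2: effect of a baseline covariate on the pain AUC.**
- Residual SD = 55 × √(1 − r²).
- SE of the difference = SD × √(2/50) = 0.2 × SD.
- Half-width = t × SE, with t = 1.9845 on 98 df unadjusted and 1.9847 on 97 df adjusted.
- Power from the noncentral t with noncentrality 38/SE.
- Equivalent unadjusted n per arm = 50/(1 − r²).

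| r (assumed) | Variance reduction | Residual SD | 95% CI half-width | Power | Equivalent n per arm |
|---|---|---|---|---|---|
| 0 | 0% | 55.0 | 21.8 | 92.8% | 50 |
| 0.1 | 1% | 54.7 | 21.7 | 93.0% | 50.5 |
| 0.2 | 4% | 53.9 | 21.4 | 93.7% | 52 |
| 0.3 | 9% | 52.5 | 20.8 | 94.8% | 55 |
| 0.4 | 16% | 50.4 | 20.0 | 96.2% | 60 |

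**Step 3: chance imbalance.** A 1.96-SE imbalance in baseline VAS is 1.96 × √(2/50) = 0.392 baseline SDs. It moves the unadjusted AUC difference by r × 0.392 × 55 = r × 21.56. For r = 0.1, 0.2, 0.3 and 0.4 that is 2.2, 4.3, 6.5 and 8.6 units, or 6% to 23% of the margin.

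**Step 4: if the true difference is not exactly zero.** Section 7b reports pilot pain means of 3.9 and 4.0. If that gap held throughout (an assumption), the AUC difference would be 0.1 × 48 = 4.8, leaving 38 − 4.8 = 33.2 to the margin. Power would be 84.8% unadjusted, 85.2% at r = 0.1, 88.0% at r = 0.3 and 90.3% at r = 0.4.

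**Step 5: QoR-15.** Variance would again fall by r², but with that instrument's own r. The documents give no QoR-15 correlation, SD, margin or power target, so nothing further can be computed.

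**The case against.** The strongest reply is that nothing in the plan is wrong. Randomisation makes the unadjusted comparison valid, and the planning SD of 55 is used without a covariate, so 50 per arm already allows for having no baseline. The gain is also small: 0.1 to 1.8 units of half-width, at most about 0.04 points of average pain. All of this stands.

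The correlation may also sit at the low end. Section 5 excludes patients using opioids for chronic pain for 4 weeks or more, so preoperative scores may cluster near zero. The worst-observation imputation after rescue makes the AUC partly a measure of rescue use. This stands too, and is why the range starts at 0.1.

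The contrast with mobility is weaker than it looks. Its baseline uses AM-PAC, whereas the postoperative scale is JH-HLM, so it is not an outcome-matched baseline. The biomarkers are the better comparison.

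A reader might infer three stronger things that the documents do not support:

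- **That imbalance in preoperative pain shifts the result one for one against the margin.** It does so only in proportion to r, and the unadjusted interval already allows for that chance variation. Open-label treatment has no bearing on chance imbalance.
- **That the trial is underpowered or biased without a baseline.** Step 1 shows that it meets its stated power.
- **That QoR-15 would gain by the same percentages as the AUC.** That would carry an assumed VAS correlation over to a different instrument.

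Finally, a baseline score gives no gain unless the model uses it. The Mann-Whitney test used for sizing cannot do so directly. The appendices and case report forms are not in the text reviewed, so a form listed only there could not be seen.

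**Conclusion.** The point holds as a modest missed gain in precision. The text schedules no preoperative VAS or QoR-15, so neither endpoint can be adjusted for the patient's own baseline, and balance on it cannot be displayed. Within the assumed range of r, the benefit for pain runs from negligible (power 93.0% at r = 0.1) to useful (96.2% at r = 0.4). It is worth more if the true difference is slightly unfavourable. These figures rest on the plan's SD of 55, on a linear model, and on every patient having a baseline; with incomplete baselines they are upper limits for the chosen r. For QoR-15 only the direction can be stated. Priority: optional, justified by its low cost.

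**What to change.** 1. **Section 4a:** add one resting VAS score and one QoR-15, completed after consent and before randomisation. Section 4a places randomisation on the day of enrolment in one paragraph and within 48 hours of surgery in another; the forms should precede whichever applies.
2. **Section 7a, pain AUC:** name baseline VAS as a fixed covariate in a linear (ANCOVA) model, in place of the open wording on covariates, and state that this model gives the confidence interval used for non-inferiority.
3. **Section 7a, QoR-15:** name baseline QoR-15 as the covariate in the comparison between arms.
4. **Missing baselines:** specify a missing-baseline indicator, which also covers patients enrolled before the change.

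**Cost:** a few minutes of patient time at the existing consent contact and one CRF page, with no added visit or procedure. The downside is some missing baselines, including all patients already enrolled.
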